## 11 DATA COLLECTION, RETENTION AND MONITORING

#### **11.1** Data Collection Instruments

The Investigator will prepare and maintain adequate and accurate source documents designed to record all observations and other pertinent data for each subject treated with the study drug.

Study personnel will enter data from source documents corresponding to a subject's visit into the protocol-specific electronic Case Report Form (eCRF) OR paper CRF when the information corresponding to that visit is available. Subjects will not be identified by name in the study database or on any study documents to be collected by the research team, but will be identified by a participant identification number.

*For eCRFs:* If a correction is required for an eCRF, the time and date stamps track the person entering or updating eCRF data and creates an electronic audit trail. *For paper CRFs:* If a correction is made on a CRF, the study staff member will line through the incorrect data, write in the correct data and initial and date the change.

The Investigator is responsible for all information collected on subjects enrolled in this study. All data collected during the course of this study must be reviewed and verified for completeness and accuracy by the Investigator. A copy of the CRF will remain at the Investigator's site at the completion of the study.

#### **11.2** Data Management Procedures

The data will be entered into a validated database. The Data Management group will be responsible for data processing, in accordance with procedural documentation. Database lock will occur once quality assurance procedures have been completed.

All procedures for the handling and analysis of data will be conducted using good computing practices meeting FDA guidelines for the handling and analysis of data for clinical trials.

#### **11.3** Data Quality Control and Reporting

After data have been entered into the study database, a system of computerized data validation checks will be implemented and applied to the database on a regular basis. The study database will be updated in accordance with the resolved queries. All changes to the study database will be documented.

#### **11.4** Archival of Data

The database is safeguarded against unauthorized access by established security procedures; appropriate backup copies of the database and related software files will be maintained. Databases are backed up by the database administrator in conjunction with any updates or changes to the database.

At critical junctures of the protocol (e.g., production of interim reports and final reports), data for analysis is locked and cleaned per established procedures.

#### **11.5** Availability and Retention of Investigational Records

The Investigator must make study data accessible to the monitor, other authorized representatives of the Sponsor (or designee), IRB/IEC, and Regulatory Agency (e.g., FDA) inspectors upon request. A file for each subject must be maintained that includes the signed Informed Consent, HIPAA Authorization and Assent Form and copies of all source documentation

related to that subject. The Investigator must ensure the reliability and availability of source documents from which the information on the CRF was derived.

All study documents (patient files, signed informed consent forms, copies of CRFs, Study File Notebook, etc.) must be kept secured for a period of seven years following completion of the study. There may be other circumstances for which the Sponsor is required to maintain study records and, therefore, the Sponsor should be contacted prior to removing study records for any reason.

#### 11.6 Monitoring

Monitoring visits will be conducted by representatives of the Sponsor according to the U.S. CFR Title 21 Parts 50, 56, and 312 and ICH Guidelines for GCP (E6). By signing this protocol, the Investigator grants permission to the Sponsor (or designee), and appropriate regulatory authorities to conduct on-site monitoring and/or auditing of all appropriate study documentation.

#### **11.7** Subject Confidentiality

In order to maintain subject confidentiality, only the participant identification number will identify all study subjects on CRFs and other documentation submitted to the Sponsor. Additional subject confidentiality issues (if applicable) are covered in the Clinical Study Agreement.

## 12 ADMINISTRATIVE, ETHICAL, REGULATORY CONSIDERATIONS

The study will be conducted according to the Declaration of Helsinki, Protection of Human Volunteers (21 CFR 50), Institutional Review Boards (21 CFR 56), and Obligations of Clinical Investigators (21 CFR 312).

To maintain confidentiality, all laboratory specimens, evaluation forms, reports and other records will be identified by a coded number and initials only. All study records will be kept in a locked file cabinet and code sheets linking a patient's name to a patient identification number will be stored separately in another locked file cabinet. Clinical information will not be released without written permission of the subject, except as necessary for monitoring by the FDA. The Investigator must also comply with all applicable privacy regulations (e.g., Health Insurance Portability and Accountability Act of 1996, EU Data Protection Directive 95/46/EC).

#### **12.1** Protocol Amendments

Any amendment to the protocol will be written by the research team. Protocol amendments cannot be implemented without prior written IRB/IEC approval except as necessary to eliminate immediate safety hazards to patients. A protocol amendment intended to eliminate an apparent immediate hazard to patients may be implemented immediately, provided the IRBs are notified.

#### **12.2** Institutional Review Boards and Independent Ethics Committees

The protocol and consent form will be reviewed and approved by the IRB/IEC of each participating center prior to study initiation. Serious adverse experiences regardless of causality

will be reported to the IRB/IEC in accordance with the standard operating procedures and policies of the IRB/IEC, and the Investigator will keep the IRB/IEC informed as to the progress of the study. The Investigator will obtain assurance of IRB/IEC compliance with regulations.

Any documents that the IRB/IEC may need to fulfill its responsibilities (such as protocol, protocol amendments, Investigator's Brochure, consent forms, information concerning patient recruitment, payment or compensation procedures, or other pertinent information) will be submitted to the IRB/IEC. The IRB/IECs written unconditional approval of the study protocol and the informed consent form will be in the possession of the Investigator before the study is initiated. The IRB/IECs unconditional approval statement will be transmitted to the Research Team prior to initiation of this study. This approval must refer to the study by exact protocol title and number and should identify the documents reviewed and the date of review.

Protocol and/or informed consent modifications or changes may not be initiated without prior written IRB/IEC approval except when necessary to eliminate immediate hazards to the patients or when the change(s) involves only logistical or administrative aspects of the study. Such modifications will be submitted to the IRB/IEC and written verification that the modification was submitted and subsequently approved should be obtained.

The IRB/IEC must be informed of revisions to other documents originally submitted for review; serious and/or unexpected adverse experiences occurring during the study in accordance with the standard operating procedures and policies of the IRB; new information that may affect adversely the safety of the patients of the conduct of the study; an annual update and/or request for re-approval; and when the study has been completed.

#### 12.3 Informed Consent Form

Informed consent will be obtained in accordance with the Declaration of Helsinki, ICH GCP, US Code of Federal Regulations for Protection of Human Subjects (21 CFR 50.25[a,b], CFR 50.27, and CFR Part 56, Subpart A), the Health Insurance Portability and Accountability Act (HIPAA, if applicable), and local regulations.

The Investigator will prepare the informed consent form, assent and HIPAA authorization and provide the documents to the Sponsor or designee for approval prior to submission to the IRB/IEC. The consent form generated by the Investigator must be acceptable to the Sponsor and be approved by the IRB/IEC. The written consent document will embody the elements of informed consent as described in the International Conference on Harmonisation and will also comply with local regulations. The Investigator will send an IRB/IEC-approved copy of the Informed Consent Form to the Sponsor (or designee) for the study file.

A properly executed, written, informed consent will be obtained from each subject prior to entering the subject into the trial. Information should be given in both oral and written form and subjects (or their legal representatives) must be given ample opportunity to inquire about details of the study. If appropriate and required by the local IRB/IEC, assent from the subject will also be obtained. If a subject is unable to sign the informed consent form (ICF) and the HIPAA

authorization, a legal representative may sign for the subject. A copy of the signed consent form (and assent) will be given to the subject or legal representative of the subject and the original will be maintained with the subject's records.

#### **12.4** Publications

The preparation and submittal for publication of manuscripts containing the study results shall be in accordance with a process determined by mutual written agreement among the study Sponsor and participating institutions. The publication or presentation of any study results shall comply with all applicable privacy laws, including, but not limited to, the Health Insurance Portability and Accountability Act of 1996.

#### **12.5** Investigator Responsibilities

By being involved in this study, the Investigators, as part of the Research Team, agrees to:

- 1. Conduct the study in accordance with the protocol and only make changes after notifying the Sponsor (or designee), except when to protect the safety, rights or welfare of subjects.
- 2. Personally conduct or supervise the study (or investigation).
- 3. Ensure that the requirements relating to obtaining informed consent and IRB review and approval meet federal guidelines, as stated in § 21 CFR, parts 50 and 56.
- 4. Report to the Sponsor or designee any AEs that occur in the course of the study, in accordance with §21 CFR 312.64.
- 5. Ensure that all associates, colleagues and employees assisting in the conduct of the study are informed about their obligations in meeting the above commitments.
- 6. Maintain adequate and accurate records in accordance with §21 CFR 312.62 and to make those records available for inspection with the Sponsor (or designee).
- 7. Ensure that an IRB that complies with the requirements of §21 CFR part 56 will be responsible for initial and continuing review and approval of the clinical study.
- 8. Promptly report to the IRB and the Sponsor (or designee) all changes in the research activity and all unanticipated problems involving risks to subjects or others.
- 9. Seek IRB approval before any changes are made in the research study, except when necessary to eliminate hazards to the patients/subjects.
- 10. Comply with all other requirements regarding the obligations of clinical investigators and all other pertinent requirements listed in § 21 CFR part 312.

## **APPENDIX B: Figures Showing Methods of Fascial Closure**

[figure not shown]
Fascial closure study, 2020 PI: [name]

Fascial closure study, 2020 PI: [name]

# Randomized to fascial closure technique

Fascial closure study, 2020 PI: [name]

#### **APPENDIX C: Pain Survey Questionnaire**

Fascial Closure – Follow-up Study Questionnaire:

Your personal ID: \_\_\_\_\_

Throughout our lives, most of us have had pain from time to time (such as minor headaches, sprains, and toothaches). Have you had pain other than these everyday kinds of pain today?

- □ Yes
- □ **No**

Did you take pain medication in the last 7 days?

[figure not shown]
- □ Yes
- □ No

I feel I have some form of pain now that requires medication each and every day.

- □ Yes
- □ **No**

If your answers to the above 3 questions were all "No", please stop here and go to the end of the questionnaire and please press "Submit". If any of the above 3 answers were "Yes", please continue.

On the diagram below, please identify the area that hurts the most.

Where would you identify this pain?

- □ Superficial (closer to the skin)
- □ Deep

Please rate the number that describes your pain level at its WORST in the last 24 hours

0 1 2 3 4 5 6 7 8 9 10

Protocol Number: FAS-101ConfidentialVersion 1.0Version Date: 25 November 2020																	
No Pin												Wo	orst pai	n you	can im	agine	
Please rate the number that describes your pain level at its LEAST in the last 24 hours.																	
	0	1	2	3	4	5	6	7	8	9	10						
No Pin												Wo	orst pai	n you	can im	agine	
Please rate the number that describes your pain level on AVERAGE.																	
	0	1	2	3	4	5	6	7	8	9	10						
No Pin												Wo	orst pai	n you	can im	agine	
Please	rate	• the	nun e	nbe	r tha	at de	scrit	nes v	our	pair	n leve	I RIGHT					
. ieuse	0	1	2	3	4	5	6	7	8	9	10			•			
No Pin			_						-	-		Wo	orst pai	n you	can im	agine	
What k	ind	of t	hings	s ma	ike y	/our	pain	fee	l be	tteri	? (i.e.	heat, n	nedicin	ie, rest	:, mass	age)?	
							·				`			,		0 /	
What k	ind	s of	thing	gs m	ake	you	r pai	n wo	orse	(i.e.	walki	ing, sta	inding,	lifting	)?		
14/1											· c.						
What t	reat	mei	nts o	r me	eaic	atior	is ar	e yo	u re	ceiv	ing to	r pain?					
													_				
In the l	ast	24 h	ours	, ho	w m	nuch	relie	ef ha	ve	bain	treatr	nents o	or med	icatio	ns prov	ided? Pl	lease identify the
percen									-						•		,
-			0%	10	)%	20%	5 3	0%	40	%	50%	60%	70%	80%	90%	100%	
No Reli	ief			C	ב					]							Complete relief
For eac				owii	ng w	ords	s, ple	ease	che	ck a	ll adje	ctives	that ap	ply to	your p	ain.	
	Ac	hing	5														
Burning																	
Dull																	
Exhausting																	
□ Gnawing																	
□ Miserable																	

 
Nagging
 
																	
□ Numb																	
		-	•														
			-														
		ooti	-														
		abbi	-														
	Tender																

Protocol Number: FAS-101 Confidential Version 1.0 Version Date: 25 November 2020 Throbbing Tiring Unbearable In the last 24 hours, how much has your pain interfered with your general activity? 6 7 Does not interfere **Completely interferes** In the last 24 hours, how much has your pain interfered with your mood? Does not interfere Completely interferes In the last 24 hours, how much has your pain interfered with your walking ability? Does not interfere **Completely interferes** In the last 24 hours, how much has your pain interfered with your normal work (includes both work outside the home and housework)? Does not interfere **Completely interferes** In the last 24 hours, how much has your pain interfered with your relations with other people? 2 3 6 7 Does not interfere Completely interferes In the last 24 hours, how much has your pain interfered with your sleep? Does not interfere П **Completely interferes** In the last 24 hours, how much has your pain interfered with your enjoyment of life? Does not interfere **Completely interferes** I prefer to take my pain medication: On a regular basis Only when necessary Do not take pain medicine I take my pain medicine (in a 24 hour period): Not every day 1 to 2 times per day 3 to 4 times per day 5 to 6 times per day 

more than 6 times per day

Do you feel you need a stronger type of pain medication?

- □ Yes
- □ No
- □ Uncertain

Other methods I use to relieve my pain include: (Please check all that apply)

- □ Warm compresses
- □ Cold compresses
- Relaxation techniques
- Distraction
- □ Biofeedback
- □ Hypnosis
- Other: \_\_\_\_\_

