	2. Two sutures, knots above rectus fascia									
	3. Two sutures, buried knots below rectus fascia									
DURATION OF SUBJECT	Subjects will be enrolled in the study for 10 weeks.									
PARTICIPATION AND	Screening: 1 day									
DURATION OF STUDY	Treatment: 1-2 days (subjects will be admitted to hospital)									
	Follow-up: 10 weeks									
	The total duration of subject recruitment time is 6 months, with									
	subsequent follow-up over a 10-week period after initial									
	recruitment.									
EFFICACY										
EVALUATIONS										
PRIMARY ENDPOINT	1. Analgesia use in first 72-hour period post-operatively.									
	2. Pain score questionnaire results over 10-week post-operative									
	period.									
STATISTICS										
Primary Analysis Plan	Statistical analysis will be undertaken using IMB ® SPSS ® Statistical									
	Software ver. 26 to undertake a two-sided T-test comparing group									
	1 vs. 2 and group 1 vs. 3 to assess for statistical significance in									
	analgesia use and pain scores.									
Rationale for Number	Based on a power of 80% at an alpha of 0.05, we estimate a 15%									
of Subjects	reduction in pain scores. As a result, we require a total of 255									
	subjects in this study. Given an estimated drop-out rate of 35%, we									
	aim to recruit a total of 350 participants.									
	In addition, sub-group analysis will be undertaken comparing pain									
	scores between primary and repeat Caesarean sections. Based on									
	the same power of 80% at an alpha of 0.05, with an estimation of a									
	15% difference in pain scores, we require a total of 140 subjects for									
	this sub-group analysis.									
L										

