### 2.1 Hypothesis

Our study hypothesises that the presence of a thicker knot in the subcutaneous layer when closing the rectus fascia leads to more irritation of the cutaneous nerves causing more sensitivity and perceived pain by the patient. In addition, we also hypothesise that by burying the knot under the rectus fascia at the angle of the rectus incisions will further diminish the level of nerve irritation in the subcutaneous layer and will allow for a further reduction in perceived pain and analgesia requirements.

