## **3** STUDY OBJECTIVES

### 3.1 Primary Objectives

The primary objective in this study is to evaluate post-operative pain in patients undergoing elective lower segment caesarean sections via a Pfannenstiel incision. The intervention in question relates specifically to the method by which the rectus fascia is closed. Participants will fill in a pain questionnaire over a period of 10 weeks at set intervals to ascertain their level of pain on visual analogue scores and requirements for analgesia.

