#### 3.2 Secondary Objectives

Our secondary objective relates specifically to whether there is a difference in pain in patients undergoing primary or repeat caesarean sections. This will also be determined using sub-group analysis of participant pain scores based upon their questionnaire responses.

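### The pain form takes no 0–10 rating from women who answer No to its three opening questions, and the plan does not say how such a form is scored

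*Combined protocol and SAP*

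**What the plan says.** The Protocol Synopsis gives the second primary endpoint as "Pain score questionnaire results over 10-week post-operative" period. Section 3.1 says the questionnaire serves "to ascertain their level of pain on visual analogue scores and requirements for analgesia". Section 7.3 schedules it on post-operative days 1 and 2 and at weeks 2, 6 and 10. Section 10.2 and the Synopsis compare groups by two-sided t-test, group 1 against 2 and group 1 against 3. The primary versus repeat Caesarean comparison in section 3.2 uses the same data: "sub-group analysis of participant pain scores based upon their questionnaire responses".

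Appendix C begins with three Yes/No questions: pain beyond the everyday kind today, "Did you take pain medication in the last 7 days", and pain now that needs medication daily. A woman with three No answers is told to "please stop here and go to the end of the questionnaire and please press" Submit. The first rating, "Please rate the number that describes your pain level at its WORST in the last 24 hours", comes after that instruction. So do the least, average and right-now ratings and the interference items, such as "how much has your pain interfered with your general activity".

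No section says whether an all-No form (three No answers, submitted) counts as 0, as missing or otherwise. No section names which rating or visit is the pain score. Section 10 promises a SAP before the final analysis; it is not among the documents.

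**The concern.** The women who skip the ratings are not random non-responders. They report no pain beyond the everyday kind and no recent medication, so they have the best outcomes on the endpoint. The skip turns on pain and medication use, and section 2.1 expects closure technique to bring a "further reduction in perceived pain and analgesia requirements". Whether a woman has a rating can therefore depend on her arm. A t-test on the ratings as recorded would leave these women out and would no longer compare the groups as randomised.

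The exposure is at weeks 6 and 10, and possibly week 2, once women have been off medication for seven days. On days 1 and 2 the scheduled oral analgesia in section 6 makes the second question a Yes for nearly everyone. Those visits and the 72-hour analgesia endpoint are therefore essentially unaffected.

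**Working it through.** **1. The plan's own figure.** Section 5.2 gives 85 per arm at 80% power and two-sided alpha 0.05. The Synopsis gives a 15% reduction. With no mean or SD stated, 85 can be inverted but not reproduced:

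- Standardised difference = (1.960 + 0.842) × √(2/85) = 0.430 (0.432 using the t distribution).
- If the 15% is relative, SD/mean = 0.15/0.432 = 0.347.

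With that ratio and assumed means of 3 to 5, only 0.5–2.5% of women score 0. Dropping all of them lowers simulated power from 77–79% to 73–76%. Those inputs put almost nobody at zero, so the figure says little about weeks 6 and 10, when many women may be pain-free.

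**2. Algebra of the skip.** Let p be the share of women with ratings and m their mean rating. With all-No forms scored 0, the mean over all respondents is p × m. A t-test on recorded ratings compares m alone. Every p and m below is assumed; differences are comparison arm minus group 1.

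- *Hidden.* p 0.70 and 0.50, m 4.0 in both. With zeros: 0.50 × 4.0 − 0.70 × 4.0 = −0.80. Recorded: 0.
- *Exaggerated.* p 0.80 in both, m 4.0 and 3.4. With zeros: 0.80 × 3.4 − 0.80 × 4.0 = −0.48. Recorded: −0.60. (Simulated with integer scores: −0.46 and −0.58.)
- *Reversed.* None/mild/moderate pain 30/40/30% and 50/20/30%, mild mean 2, moderate mean 5. With zeros: (0.2 × 2 + 0.3 × 5) − (0.4 × 2 + 0.3 × 5) = 1.9 − 2.3 = −0.40. Recorded: 1.9/0.5 − 2.3/0.7 = 3.80 − 3.29 = +0.51.
- *Shrunk.* Simulated latent normal pain, means 0.5 and −0.5, SD 2, rounded and cut to 0–10. With zeros: −0.50. Recorded: −0.30.
- *No effect.* Identical arms in the same latent model (mean 0.5, SD 2): no bias, and rejection of 4.9% with zeros and 4.8% on recorded ratings.

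**3. Power in the hidden case.** 85 per arm, SD 1.5 among raters. With zeros, variance = p(SD² + m²) − (pm)²:

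- Group 1: 0.70 × 18.25 − 2.8² = 4.935.
- Comparison arm: 0.50 × 18.25 − 2.0² = 5.125.
- Standard error = √((4.935 + 5.125)/85) = 0.344, and 0.80/0.344 = 2.33.
- Power ≈ Φ(2.33 − 1.96) ≈ 64%; simulation with integer scores gives 63%.

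On recorded ratings there is no difference to find, so rejection is 5%.

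**4. Dependence on the substituted score.** In the hidden case, scoring all-No forms k gives a difference of −0.20 × (4 − k): −0.80, −0.60 and −0.40 for k = 0, 1 and 2.

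**The case against.** The strongest reply is that the protocol never says all-No forms will be dropped. The bottom anchor of the scale means no pain, so 0 is the natural reading of such a form, and the promised SAP may say so. Much of this stands. A reader might infer that the plan excludes pain-free women, but the documents do not say that. Omission is only what a t-test does by default when no rule is written. A SAP can supply the rule, though it cannot recover ratings that were never asked for. Nor is 0 exact for every item: the first question sets aside everyday pain and asks about today, worst and least pain cover 24 hours, and the average item states no period.

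A reader might also infer that the form by itself produces false positives. It does not: if closure has no effect, the skip removes the same kind of women from each arm and rejection stays near 5%.

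The larger effects rest on chosen inputs; the reversal in particular needs a specific shift from mild pain to none. That is correct, and they show only what is possible. The point also depends on which visit defines the pain score: if only days 1 and 2 were compared, it would be negligible. The Synopsis endpoint, however, runs over 10 weeks.

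Finally, simply moving the ratings ahead of the stop instruction would let everyday pain be rated. That is a fair criticism, and the fix has to deal with it.

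**Conclusion.** The point holds and should be fixed. Confidence is high on two facts: an all-No form carries no 0–10 rating, and no scoring rule is stated. It does not extend to the direction or size of any bias.

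The consequence has two conditions: all-No forms are left out of the t-test, and closure affects pain or medication use. When both hold, the recorded difference at weeks 6 and 10, and possibly week 2, can be hidden, shrunk, exaggerated or reversed. The documents give no pain-free share, mean or SD, so no single size can be stated. The fall from about 63% to 5% power is an illustration under assumed inputs, and it would be wrong to read it as the expected loss in this trial.

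**What to change.** 1. State in section 10.2, before the database lock and unblinding described in section 7.2, that a submitted all-No form scores 0 on the pain rating analysed and stays in the comparison. Keep it distinct from an unreturned form, which matters with 35% drop-out expected. Report the all-No share by arm and visit.

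2. Preferably also amend the form, with IRB/IEC approval under sections 12.1 and 12.2, so that every respondent gives the 0–10 ratings. Word them to refer to pain from the Caesarean, so that the everyday pain set aside by the first question is not rated. If both form versions exist, use entered ratings where available and 0 for all-No forms collected on the present version.

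3. Optionally, repeat the comparison with a small non-zero score for all-No forms.

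The first step costs a few sentences. The second costs an amendment, a slightly longer form for pain-free women and possibly two form versions. Including the zeros can lower power at later visits. In the assumed case with 20% all-No in both arms, simulated power is 32% with zeros and 62% on recorded ratings, but the higher figure refers to an exaggerated difference in a selected group.
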